6.8. Previous and Concomitant Therapy

Medication/therapy will be classified into Anatomical Therapeutic Chemical (ATC) drug classes using the latest version of the World Health Organization (WHO) drug dictionary.

Table RHCG.6.4. Previous and Concomitant JIA Therapies Grouping

Drug Class	Previous	Concomitant
csDMARDs	Yes	Yes
Oral corticosteroids	Yes	Yes
NSAIDs including cyclooxygenase-2 inhibitors	Yes	Yes
Analgesics	Yes	Yes
Biologics (bDMARDs)	Yes	No

Abbreviations: bDMARDs: biologic disease-modifying antirheumatic drugs; csDMARDs = conventional synthetic disease-modifying antirheumatic drugs; JIA = juvenile idiopathic arthritis; NSAID = nonsteroidal anti-inflammatory drug.

A by-patient listing of previous and concomitant therapy, and a by-patient listing of previous JIA therapy for the ITT Population will be provided.

6.8.1. Previous Therapy

Previous therapy is defined as the therapy that starts and ends prior to the date of first dose of study treatment in the OLT Period. If a patient does not receive a treatment drug, the first dose date of the study will be replaced with the date of randomization. If therapy start and/or end dates

are missing or partial, the dates will be compared as far as possible with the date of first dose of study treatment in the OLT Period. If there is clear evidence to suggest that the therapy stopped prior to the first dose of study treatment in the OLT Period, the therapy will be assumed to be previous only.

A list of previous JIA therapies is found in [Table RHCG.6.4](#).

The number and percentage of patients who received previous therapy for JIA, as recorded on the *Prior Therapy: Juvenile Idiopathic Arthritis (CM2001_LV1)* eCRF page will be summarized by treatment group, overall and preferred name. The number and percentage of patients with each reason for discontinuing previous therapy for JIA will also be presented by treatment group.

Previous therapy for JIA will be summarized for the ITT Population.

6.8.2. Concomitant Therapy

Concomitant therapy for treatment period is defined as the therapy that starts before, on, or after the first day of study treatment in treatment period and before the last visit date in the treatment period, and continues into the treatment period, that is, either no end date (the therapy is ongoing) or an end date on or after the first day of study treatment in treatment period. If patient does not receive a treatment drug, the first day of the study treatment will be replaced with the date of randomization. Note, concomitant therapy will belong to a treatment period if the therapy starts and ends on the exact same day as the first day of study treatment of the treatment period.

A list of concomitant JIA therapies is found in [Table RHCG.6.4](#).

If a partial or completely missing medication start date/time or end date/time is present, the following imputation rules will be utilized in the analysis:

- For the start date:
 - If year, month, and day are missing, then use the earlier of the patient's first visit date or the consent date.
 - If either month or month and day are missing, then use January 1.
 - If only day is missing, impute the first day of the month.
- For the start time:
 - Impute as 23:59
- For the end date:
 - If year, month, and day are missing, then use the patient's last visit date.
 - If either month or month and day are missing, then use December 31.
 - If only day is missing, then use the last day of the month.
 - The imputed date will not be beyond the patient's last visit date.
- For the end time:
 - Impute as 23:59
- If there is any doubt, the medication will be flagged as concomitant.

Concomitant will be summarized and analysed for the following populations:

- ITT Population (OLT Period)

- OLE Period Population and OLE Switcher Population (OLE Period), and
- LTE Period (LTE Safety Population).

6.9. Efficacy Analyses

6.9.1. Primary Outcome and Methodology

The analysis methods and analysis periods are described in [Table RHCG.6.5](#) and [Table RHCG.6.6](#).

The primary efficacy endpoint is the percentage of ixekizumab-treated patients meeting JIA ACR30 response criteria at Week 16. A JIA ACR30 response is defined as at least 30% improvement from baseline in at least 3 of any 6 variables in the core set, with no more than 1 of the remaining variables worsening by >30%.

The individual components that make up the JIA ACR30 core set variables are defined as follows:

- Number of active joints in 73 joints (active joint defined as a joint that is swollen, or in the absence of swelling, has loss of passive motion accompanied by either pain on motion or joint tenderness)
- Number of joints with limited range of motion in 69 joints
- Physician's Global Assessment of Disease Activity (21-circle Visual Analogue Scale [VAS])
- Parent's Global Assessment of Well-Being
- Physical function as assessed by the Childhood Health Assessment Questionnaire (CHAQ)
- Erythrocyte sedimentation rate (ESR)

A listing of the primary efficacy endpoint will be provided.

If the study is not stopped for futility, the posterior probability of the Week 16 JIA ACR30 response rate exceeding 50% will be calculated, and the study objective will be successfully met (i.e., a positive study) if this posterior probability is at least 80%.

The beta-binomial 2-stage Bayesian model will be used for the primary analysis. The beta shape parameters are:

- a : the degree of response
- b : the magnitude of non-response

The prior distribution of the JIA ACR30 response rate at Week 16, p , is:

$$p \sim \text{beta}(a, b)$$

where a and b are the prior parameters and have an intuitive interpretation of prior responders and non-responders, respectively. The prior will be pre-specified with parameters $a = b = 1/2$, which is largely accepted as a Jeffery prior.

Let $X_i|p$ be the JIA ACR30 response at Week 16 of the i^{th} patient treated with ixekizumab. X_i conditionally follows a Bernoulli distribution:

$$X_i|p \sim \text{Bernoulli}(p).$$

The number of JIA ACR30 responders at Week 16, K is binomial:

$$K|p \sim \text{binomial}(n, p)$$

where n is the sample size of the ixekizumab patients of the ITT population in the study.

Due to conjugacy in the beta-binomial model, the posterior distribution of p is:

$$p|k \sim \text{beta}(a + k, b + n - k)$$

The posterior mean, variance, and 95% credible interval will be summarized from this posterior distribution. The following will be provided:

- The posterior mean,

$$\mu_p = \frac{a + k}{a + b + n}$$

- The posterior standard deviation,

$$\sigma_p = \sqrt{\frac{(a + k)(b + n - k)}{(a + b + n)^2(a + b + n + 1)}}$$

- 95% credible interval, which will include the 2.5th and 97.5th percentiles of the posterior distribution

The beta posterior probability of the response rate exceeding 0.5 is given by:

$$\begin{aligned} P(p > 0.5|k) &= \int_{0.5}^1 \frac{1}{B(a + k, b + n - k)} p^{a+k-1} (1 - p)^{b+n-k-1} dp \\ &= \int_{0.5}^1 \frac{1}{B\left(\frac{1}{2} + k, \frac{1}{2} + n - k\right)} p^{k-1/2} (1 - p)^{n-k-1/2} dp \end{aligned}$$

where:

$$B(\alpha, \beta) = \int_0^1 t^{\alpha-1} (1 - t)^{\beta-1} dt$$

$$\alpha > 0, \beta > 0$$

is the beta function.

The following example and SAS® code illustrate how the posterior probability is obtained.

```
%macro bayesian_algo (p_0=, a=, b=, k=, n=);
  data bayesian;
    p=&k/&n;
    a_post=&a+&k;
```

```
b_post=&b+&n-&k;
k=&k;
n=&n;
h_0=&k/&n;
h_1=1-&k/&n;
x1=probbeta(h_0,a_post,b_post);
x2=1-probbeta(h_1,a_post,b_post);
postProb=1-probbeta(&p_0,a_post,b_post);

run;
%mend bayesian_algo;

%bayesian_algo(p_0=0.5,a=0.5,b=0.5,k=35,n=80);
```

Table RHCG.6.5. Description and Derivation of Primary Efficacy Endpoint

Measure	Description	Variable	Derivation/Comment	Imputation Approach if with Missing Components
JIA ACR30 Responder Index	Juvenile Idiopathic Arthritis American College of Rheumatology, JIA ACR, is comprised of 6 variables: active joint count, limitation of motion joint count, physician global assessment, patient/parent global assessment, Childhood Health Assessment Questionnaire (CHAQ), and acute-phase reactant level (ESR). A JIA ACR30 response is defined as at least 30% improvement from baseline in at least 3 of any 6 variables in the core set, with no more than 1 of the remaining variables worsening by more than 30% (Giannini et al. 1997).	Proportion of patients with Juvenile Idiopathic Arthritis American College of Rheumatology (JIA ACR) 30 at Week 16, nonresponder imputation (NRI)	See Section 6.9.1 and Appendix 1	See Appendix 1

Abbreviations: ACR = American College of Rheumatology; ESR = erythrocyte sedimentation rate; JIA = Juvenile Idiopathic Arthritis; NRI = nonresponder imputation.

Table RHCG.6.6. Description of Analysis Period and Analysis Method of Primary Efficacy Endpoint

Measure	Variable	Population	Analysis Timepoint	Analysis Method
JIA ACR30 Responder Index	Proportion of patients with JIA ACR30	ITT	Week 16	Bayesian statistics

Abbreviations: ACR = American College of Rheumatology; JIA = Juvenile Idiopathic Arthritis.

6.9.2. Secondary Efficacy Analyses

Secondary efficacy analyses will be based on each treatment period with the respective population at each visit. A listing of each secondary efficacy analysis may be provided. The analysis methods and analysis periods are described in [Table RHCG.6.7](#) and [Table RHCG.6.8](#).

Table RHCG.6.7. Description and Derivation of Secondary Efficacy Endpoints

Measure	Description	Variable	Derivation/Comment	Imputation Approach if with Missing Components
JIA ACR Responder Index	Juvenile Idiopathic Arthritis American College of Rheumatology (JIA ACR), is comprised of 6 variables: active joint count, limitation of motion joint count, physician global assessment, patient/parent global assessment, Childhood Health Assessment Questionnaire (CHAQ), and acute-phase reactant level (ESR). JIA ACRx response is defined as at least $x\%$ improvement from baseline in at least 3 of any 6 variables in the core set, with no more than 1 of the remaining variables worsening by more than $x\%$. x is a number from 0 to 100.	Juvenile Idiopathic Arthritis American College of Rheumatology (JIA ACR) 30/50/70/90/100	See Section 6.9.1 and Appendix 1	See Appendix 1
Active joint count	Number of active joints (defined as a joint that is swollen or in the absence of swelling has loss of passive motion accompanied by either pain on motion or joint tenderness) in 73 joints.	Change from baseline of active joint count	Calculation: Change from baseline: observed active joint count at visit minus baseline active joint count	Missing if baseline or post-baseline value is missing.
Limited range of motion joint count	Number of joints with limited range of motion in 69 joints	Change from baseline of limited of motion joint count	Calculation: Change from baseline: observed limited range of motion joint count at visit minus baseline limited range of motion joint count	Missing if baseline or post-baseline value is missing.
Physician's global assessment of disease activity (VAS)	The Physician's Global Assessment of Disease Activity is used to assess the patient's current disease activity, as it relates to their signs and symptoms. The instrument uses a 21 circle VAS ranging from 0 to 10 (using 0.5 increments) where 0 = "no activity" and 10 = "maximum activity" (Filocamo et al. 2010).	Change from baseline of physician's global assessment of disease activity	Calculation: Change from baseline: observed score at visit minus baseline score	Missing if baseline or post-baseline value is missing.

Measure	Description	Variable	Derivation/Comment	Imputation Approach if with Missing Components
Parent's global assessment of overall well-being measured by CHAQ (0-100 mm VAS)	The parent is generally asked to make a global assessment of the child's overall well-being on a 100 mm VAS, with anchors of '0 = very good' and '100 = very poor', which is located at the bottom of the CHAQ	Change from baseline of parent's global assessment of overall well-being	The detail of physical function calculation is documented in Appendix 3 Calculation: Change from baseline: observed score at visit minus baseline score	Missing if baseline or post-baseline value is missing.
Physical function as measured by CHAQ (0-3)	The CHAQ assesses health status and physical function over the past week in children with juvenile arthritis over the past week, which the parent or legal guardian completes, regardless of the age of the patient. Physical function is measured by CHAQ from disability index. The Disability Index contains 30 items grouped into the following 8 domains (not including assistive devices/aids questions): physical function, dressing, and grooming (4 items), arising (2 items), eating (3 items), walking (2 items), hygiene (5 items), reach (4 items), grip (5 items), and activities (5 items). Each item is scored from 0 to 3 (0 = no difficulty; 1 = some difficulty; 2 = much difficulty; 3 = unable to do or not applicable) (Singh et al. 1994). The total score is the average of domain score, which is range from 0 to 3. At least 6 domains are required in calculation.	CHAQ – Physical Function Score Change from baseline of physical function	The detail of physical function calculation is documented in Appendix 3 Change from baseline: observed score at visit minus baseline score	Missing if baseline or post-baseline value is missing.

Measure	Description	Variable	Derivation/Comment	Imputation Approach if with Missing Components
ESR (mm/hr)	An erythrocyte sedimentation rate (ESR) is a type of blood test that measures how quickly erythrocytes (red blood cells) settle at the bottom of a test tube that contains a blood sample. Normally, red blood cells settle relatively slowly. A faster-than-normal rate may indicate inflammation in the body.	Change from baseline of ESR	Calculation: Change from baseline: observed lab value at visit minus baseline lab value	Missing if baseline or post-baseline value is missing.
Disease flare	Disease flare is defined as a worsening of $\geq 30\%$ in at least 3 of the 6 JIA ACR core criteria for JIA and an improvement of $\geq 30\%$ in no more than 1 of the criteria from the patient's condition at randomization baseline. More information on Disease Flare can be found in Appendix 2 .	Disease Flare	The detail of disease flare calculation is documented in Appendix 2 .	See Appendix 2 for more details.
PASI	Psoriasis Area and Severity Index (PASI): For patients with plaque psoriasis, combines assessments of the extent of body-surface	PASI total score Change from baseline	The composite PASI score is calculated by multiplying the sum of the individual-severity scores for each area	If any individual score is missing, the PASI score will not be

Measure	Description	Variable	Derivation/Comment	Imputation Approach if with Missing Components
	
involvement in 4 anatomical regions (head and neck, trunk, arms, and legs) and the severity of scaling (S), redness (R), and plaque induration/infiltration thickness (T) in each region, yielding an overall score of 0 for no psoriasis to 72 for the most severe disease (Fredriksson and Pettersson 1978). Severity is rated for each index (R, S, T) on a 0-4 scale (0 for no involvement up to 4 for severe involvement):
 
 0 = none 1 = slight 2 = moderate 3 = severe 4 = very severe 
The body is divided into 4 anatomical regions comprising the head (h), upper limb (u), trunk (t), and lower limb (l). In each of these areas, the fraction of total BSA affected is graded on a 0-6 scale (0 for no involvement; up to 6 for 90% to 100% involvement):
 
 0 = 0% (clear) 1 = >0% to <10% 2 = 10% to <30% 3 = 30% to <50% 4 = 50% to <70% 5 = 70% to <90% 6 = 90% to 100% 
The various body regions are weighted to reflect their respective proportion of BSA.
	
in PASI total score
 
% Improvement in PASI total score
	
by the weighted area-of-involvement score for that respective area, and then summing the 4 resulting quantities as follows:
 $\text{PASI} = 0.1(R_h + T_h + S_h)A_h + 0.2(R_u + T_u + S_u)A_u + 0.3(R_t + T_t + S_t)A_t + 0.4(R_l + T_l + S_l)A_l$ 
Where,
 
R_h, R_u, R_t, R_l = redness score of plaques on the head, upper limb, trunk, and lower limb, scored 0-4 respectively;
 
T_h, T_u, T_t, T_l = thickness score of plaques on the head, upper limb, trunk, and lower limb, scored 0-4 respectively;
 
S_h, S_u, S_t, S_l = scaliness score of plaques on the head, upper limb, trunk, and lower limb, scored 0-4 respectively;
 
A_h, A_u, A_t, A_l = numerical value translation of % area of psoriatic involvement score for the head, upper limb, trunk, and lower limb, respectively
 
PASI scores are treated as a continuous score, with 0.1 increments within these values.
	
calculated, hence missing.
 
Change from baseline in PASI is missing if baseline or observed value are missing
 
% Improvement in PASI total score is missing if baseline or observed value are missing

Measure	Description	Variable	Derivation/Comment	Imputation Approach if with Missing Components

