Appendix 3. Algorithm for Calculating the CHAQ

The Childhood Health Assessment Questionnaire (HAQ) has been adapted from the Stanford Health Assessment Questionnaire. The Stanford HAQ assesses four outcome dimensions: disability, discomfort and pain, drug side effects, and dollar costs. Disability is measured in the categories of dressing, arising, eating, walking, hygiene, grip, and activities. Discomfort is determined by the presence of pain and its severity. The HAQ is either parent- or self-administered. Parents are reliable proxy-reporters for their child's functional status, describe below is the parent-administered format. Parents are given the questionnaire and asked to complete it without additional instructions.

Disability Index – Daily Function

General Description:

This section is designed to assess the patient's functional ability over the past week. It is composed of eight domains, each of which has at least two component questions. Parents are also asked to indicate the use of any aids or devices or if the child needs help from another person for any of these activities.

The eight domains are: dressing and grooming, arising, eating, walking, hygiene, reach, grip, and activities. For each of these domains, parents are asked to record the amount of difficulty their child may have. Parents are requested to note only those difficulties that are caused by arthritis.

The time frame is over the past week. By repeating the questionnaire at specific time periods we can look at the patterns of function.

Scoring and Coding:

Possible responses for the component questions are:

Without any difficulty = 0

With some difficulty = 1

With much difficulty = 2

Unable to do = 3.

The patient must have a score for at least 6 of the 8 domains. If there are less than six domains completed, a CHAQ cannot be computed. The highest score for any component question determines the score for that category. If a component question is left blank, then the score for that category is determined by the remaining completed question(s). If all component questions are blank, then the category is left blank.

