If either devices and/or help from another person is checked for a category, the score = 2. This may determine the score unless the score on any other component question = 3. For example, the response to "Dress yourself..." is with Some difficulty (score = 1). The parent has checked the use of a device for dressing, thereby increasing the score to 2. The response to "Shampoo your

hair" is Unable to do (score = 3). Therefore, the score for the Dressing category is 3. The index is calculated by adding the scores for each of the domains and dividing by the number of domains answered. This gives a score in the 0 to 3.0 range.

Devices associated with each category:

CHAQ Category	Companion aids or devices item
Dressing and Grooming	Devices used for dressing (button hook, zipper pull, long handled shoe horn, etc.)
Arising	Built up or special chair
Eating	Built up or special utensils
Walking	Cane, walker, crutches, wheelchair
Hygiene	Raised toilet seat, bathtub seat, bathtub bar, long-handled appliances in bathroom
Reach	Long handled appliances for reach
Grip	Jar opener (for jars previously opened)

Devices written in the "Other" sections are considered only if they would be used for any of the stated domains.

Discomfort – Index or VAS

General Description:

This question is designed to obtain information about the presence or absence of arthritis-related pain and its severity. The time frame is in the past week. The Discomfort Index of the CHAQ includes (Ruperto et al. 2001):

- Parent's Global Assessment of Well-being
 - This is a component of the JIA ACR 30 core response set
 - The instrument uses a 0 to 100 mm VAS where 0 = "very well" and 100 = "very poor"
- Pain assessment due to illness
 - The question uses a 0 to 100 mm VAS where 0 = "no pain" and 100 = "very severe pain"

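### 'Not applicable' CHAQ items are scored 3 in protocol 9.1.3.1 and SAP Table RHCG.6.7 but have no code in Appendix 3; combined with highest-item scoring, the code of 3 can distort a primary-endpoint component

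*SAP*

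**What the plan says.** Protocol 9.1.3.1 and the Description column of SAP Table RHCG.6.7 (row for physical function) define the top item score in the same way: "3 = unable to do or not applicable". The Derivation column of that row does not use this code. It says "The detail of physical function calculation is documented in Appendix 3".

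Appendix 3 lists four responses scored 0 to 3, with 3 for 'unable to do'. It has no code for 'not applicable'. Its other rules are:

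- "Parents are requested to note only those difficulties that are caused by arthritis".
- "The highest score for any component question determines the score for that category".
- A blank item is skipped, and the domain takes its score from the items that were answered.
- "The patient must have a score for at least 6 of the 8 domains".
- "The index is calculated by adding the scores for each of the domains and dividing by the number of domains answered".

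SAP 6.9.1 lists CHAQ physical function among the six JIA ACR30 core variables. Under Appendix 1 a component counts as improved at a change of -30% or lower. A responder needs at least three improved components and no more than one that worsens by over 30%.

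**The concern.** The documents answer the same scoring question in two ways. A programmer who follows Table RHCG.6.7 codes 'not applicable' as 3. A programmer who follows Appendix 3 finds no such code, and the nearest rule is to skip the item. No text says which prevails.

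The code of 3 also conflicts with what Appendix 3 sets out to measure. An item that does not apply to a child is not a difficulty caused by arthritis, yet it would be scored as the worst possible disability. Because the highest item sets the domain, the child's other answers in that domain would no longer count.

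JPsA participants are eligible from age 2 (protocol 6.1), and protocol 3.2 describes an early JPsA peak at 2 to 4 years, so it is plausible that some items will not apply to some participants. The score feeds the Week 16 primary endpoint, the secondary CHAQ change and disease flare (Appendix 2). The final success rule is a sharp count, so the status of individual patients can matter if the result falls near the boundary.

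**Working it through.** The documents give no figure for this scoring point, so there is none to reproduce. The check applies their own rules.

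**Inputs.** Eight domains scored 0 to 3, highest item sets the domain, index = sum of domain scores / domains answered (Appendix 3); 'not applicable' = 3 (Table RHCG.6.7, protocol 9.1.3.1); improvement threshold -30% (Appendix 1).

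**Set-up.** Let *k* domains be held at 3 at both visits by a 'not applicable' item. Let the other domains sum to *T* at baseline. All eight domains are scored, so the divisor cancels.

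1. *Effect on the index.* A held domain that would otherwise score 0 adds 3/8 = 0.375. If it would otherwise score *s*, it adds (3 - *s*)/8.
2. *Largest possible improvement* (other domains fall to 0): *T*/(*T* + 3*k*).
3. *Reduction needed in the other domains to reach 30%:* 0.3(*T* + 3*k*)/*T*. This exceeds 100% when *T* < 9*k*/7.

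| *k* | *T* | Largest improvement | Reduction needed in the other domains |
|---|---|---|---|
| 1 | 1 | 1/4 = 25% | not reachable |
| 1 | 2 | 2/5 = 40% | 0.3 × 5/2 = 75% |
| 1 | 4 | 4/7 = 57.1% | 0.3 × 7/4 = 52.5% |
| 1 | 6 | 6/9 = 66.7% | 0.3 × 9/6 = 45% |
| 1 | 7 (seven domains at 1) | 7/10 = 70% | 0.3 × 10/7 = 42.9% |
| 1 | 14 (seven domains at 2) | 14/17 = 82.4% | 0.3 × 17/14 = 36.4% |
| 2 | 2 | 2/8 = 25% | not reachable |
| 2 | 4 | 4/10 = 40% | 0.3 × 10/4 = 75% |

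Without a held domain the reduction needed is always 30%.

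**Item 'not applicable' at both visits, one held domain.**

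- Other domains 4 to 2: 7/8 to 5/8, a change of -2/7 = -28.6%, not improved. With the item blank: 4/8 to 2/8 (or 4/7 to 2/7 if the whole domain is blank), -50%, improved.
- Other domains 6 to 4: -2/9 = -22.2% instead of -2/6 = -33.3%. The classification changes.
- Other domains 6 to 3: -3/9 = -33.3% instead of -50%. It counts as improved either way.

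**Item 'not applicable' at one visit only, other domains unchanged at 4.**

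- Baseline only: 7/8 to 4/8, -3/7 = -42.9%, a false improvement.
- Week 16 only: 4/8 to 7/8, +3/4 = +75%, a false worsening.

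**Effect on worsening.** Other domains rising from 3 to 4 is +33.3% and counts as worsening. With one domain held it is 6 to 7, +16.7%, and does not count.

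**Boundary of the success rule.** SAP 6.15.1 requires fewer than 37 nonresponders, so at least 80 - 36 = 44 responders out of 80. With the Beta(0.5, 0.5) prior, the posterior probability of a rate above 50% is 0.814 at 44 responders and 0.749 at 43, which agrees with the stated rule.

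**The case against.** The strongest reply is that Appendix 3 is the designated algorithm, that the disputed code sits only in descriptive text, and that the primary derivation (SAP 6.9.1 and Appendix 1) never mentions 'not applicable'. On that view a domain is held at 3 only if someone combines two places that were never meant to be combined. This is fair as to how the distortion arises. It does not settle the matter: Appendix 3 is silent on 'not applicable', and the only two places that assign it a score say 3.

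Three stronger readings are tempting, and the documents do not support them.

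- *One 'not applicable' item blocks CHAQ improvement.* A reader might infer this from the highest-item rule. With one held domain it is true only for *T* of 0 or 1. At *T* = 0 it scarcely matters: the CHAQ baseline without the held domain would be 0, Appendix 1 would then treat CHAQ as missing, and three of the same five other components would still have to improve. A ceiling below 30% at higher baselines needs several held domains. For example, four held with the other four at 1 gives 4/(4 + 12) = 25%. Nothing in the documents suggests such counts are usual.
- *Young children are biased towards nonresponse.* This assumes the item is 'not applicable' at both visits. If it is so at one visit only, the error can go either way, and a held domain also hides worsening that could disqualify a responder.
- *The primary result is materially affected.* The documents give neither the frequency of 'not applicable' answers nor the expected number of very young participants, and ERA participants must be at least 6. No change in the response rate can be derived.

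Both texts attribute the item coding to a cited instrument paper that is not available here, so whether 3 or blank matches the questionnaire version in use cannot be decided from the documents.

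**Conclusion.** The conflict is real and should be resolved. Taken with the highest-item rule, the stated code scores an answer unrelated to arthritis as maximum disability in one of six primary-endpoint components.

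For one held domain, the size is up to 0.375 on the index per visit, a complete block on 30% improvement only when the other seven domains sum to 1 or less, and otherwise a raised bar (75% reduction needed at a sum of 2, 52.5% at 4, 45% at 6). The direction is not fixed, because a 'not applicable' answer at a single visit can produce false improvement or false worsening.

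JIA ACR30 status changes only for patients at the margin: those for whom CHAQ decides whether three components improved, or whether a second one worsened. The examples assume that all eight domains are scored and that the held domain has no other difficulty. How many participants are affected is unknown.

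**What to change.** State one rule for 'not applicable' in protocol 9.1.3.1, SAP Table RHCG.6.7 and SAP Appendix 3, checked against the questionnaire version in use.

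- Where 'not applicable' is recorded separately from 'unable to do', score it as blank. Appendix 3's remaining-items and 6-of-8-domain rules then apply unchanged.
- Report Week 16 JIA ACR30 under the other coding (3) as a sensitivity analysis, with the number of participants who have any 'not applicable' item at baseline or Week 16.
- If the two answers share one response option, the recoding cannot be applied to the collected data. In that case say so and write the code of 3 into Appendix 3 as the single rule.

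The cost is a line or two in each of the three places and one extra analysis. The sample size does not change, and no new data are needed if the answers are recorded separately. The downside is that a few young children may have fewer than 6 scored domains and so no CHAQ score. Appendix 1 already covers that: a component missing at baseline is dropped from the core set, and one missing after baseline is carried forward within the period.
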